4 SELECTION AND WITHDRAWAL OF SUBJECTS

4.1 Inclusion Criteria

Subjects who meet all of the following criteria will be eligible to participate in the study:

1. Women >40 years and ≤65 years of age at the screening visit;
2. A body mass index between 18 kg/m² to 38 kg/m² (extremes included);
3. Spontaneous amenorrhea for ≥12 consecutive months; or spontaneous amenorrhea for ≥6 months with biochemical criteria of menopause FSH >40 IU/L); or having had bilateral oophorectomy ≥6 weeks prior to the screening visit (with or without hysterectomy);
4. At least 50 moderate to severe vasomotor symptoms per week (ie, 7 consecutive days), as recorded in the daily diary during the screening period;
5. In good general health as determined on the basis of medical history and general physical examination, including a bimanual clinical pelvic examination and clinical breast examination devoid of relevant clinical findings, performed at the screening visit; hematology and biochemistry parameters, pulse rate and/or blood pressure, and ECG within the reference range for the population studied, or showing no clinically relevant deviations, as judged by the Investigator;
6. Women >40 years of age who have documentation of a normal/negative or no clinically significant findings mammogram (obtained at screening or within the prior 9 months of trial enrollment). Appropriate documentation includes a written report or an electronic report indicating normal/negative or no clinically significant mammographic findings;
7. Willing to undergo a transvaginal ultrasound to assess endometrial thickness at screening and at Week 12 (end-of-treatment), and for subjects who are withdrawn from the study prior to completion, at the Early Termination (ET) Visit. This is not required for subjects who have had a partial (supracervical) or full hysterectomy;
8. Willing to undergo an endometrial biopsy at screening (in the event that the subject's transvaginal ultrasound shows endometrial thickness ≥4 mm) and at Week 12 (end-of-treatment – all subjects), for subjects with uterine bleeding, and, for subjects who are withdrawn from the study prior to completion, at the ET Visit if study drug exposure is ≥10 weeks. This is not required for subjects who have had a partial (supracervical) or full hysterectomy;
9. Negative alcohol breath test and negative urine test for selected drugs of abuse (amphetamines, tricyclic antidepressants, cocaine, or opiates) at the screening visit;

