9.18 Endometrial Biopsy

Subjects will undergo endometrial biopsy (Pipelle) at the following timepoints:

- At screening, if endometrial thickness is ≥ 4 mm determined by transvaginal ultrasound;
- At Week 12 (end-of-treatment) – all subjects;
- At the ET Visit for subjects who are withdrawn from the study prior to completion, if exposure to study drug is ≥ 10 weeks; and
- In all cases of uterine bleeding.

Although the transvaginal ultrasounds (see Section 9.17) will be read centrally, a local transvaginal ultrasound reading at screening should guide the decision to perform endometrial biopsy or not. In the event the local reader measures an endometrial thickness ≥ 4 mm, a single biopsy will be taken from the thickest part of the endometrium. Refer to the FDA draft guidance.²³ In the event an inadequate specimen is obtained at screening, 1 repeat biopsy may be performed if technically possible. If the biopsy is abnormal at Week 12 (end-of-treatment), subjects will have a repeat biopsy 4 weeks later, if clinically indicated. All biopsies will be read by centrally by a blinded pathologist.

In the event that subject's biopsy indicates hyperplasia, biopsies will be assessed by 2 additional blinded pathologists. The participating study pathologists will be from different institutions with independent fiduciary and organizational reporting and will be blinded to each other's assessments. Concurrence of 2 of the 3 pathologists will be accepted as the final diagnosis. If the 3 pathologists do not agree, the most severe pathologic diagnosis would be used as the final diagnosis.

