5.1 Safety Analysis Set (SAF)

The SAF comprises all randomized subjects who received at least one dose of study drug. The SAF will analyze patients as treated. In case a subject erroneously received a treatment different from her randomized treatment, the subject will be assigned to the treatment group

that the subject received as first dose. The SAF will be used for summaries of demographic and baseline characteristics and all safety and tolerability related variables.

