7.5 Analysis of Safety

All analyses of safety will be presented by treatment group for SAF, unless specified otherwise. For analyses by visit, the visit windows from Section 7.10.6 will be applied. Except for adverse events and follow-up visit data, only data up to one day after the last dose date will be considered for the analyses.

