7.5.1 Adverse Events

Summaries and listings of SAEs and Serious TEAEs include SAEs upgraded by the sponsor based on review of the Sponsor's list of Always Serious terms if any upgrade was done.

The coding dictionary for this study will be MedDRA. It will be used to summarize AEs by SOC and PT.

An overview table will include the following details:

- Number of TEAEs,
- Number and percentage of subjects with TEAEs,
- Number of drug related TEAEs,
- Number and percentage of subjects with causally drug related TEAEs,
- Number of serious TEAEs,
- Number and percentage of subjects with serious TEAEs,
- Number of serious drug related TEAEs,
- Number and percentage of subjects with serious drug related TEAEs,
- Number of TEAEs leading to permanent discontinuation of study drug,
- Number and percentage of subjects with TEAEs leading to permanent discontinuation of study drug,
- Number and percentage of subjects with TEAEs leading to study drug interruption, and
- Number of deaths.

The number and percentage of subjects with TEAEs, as classified by SOC and PT will be summarized for each treatment group. Summaries will be provided for:

- TEAEs,
- drug related TEAEs,
- serious TEAEs,
- drug related serious TEAEs,

- TEAEs leading to permanent discontinuation of study drug,
- drug related TEAEs leading to permanent discontinuation of study drug,
- TEAEs excluding serious adverse events that equal to or exceed a threshold of 5% in any treatment group, and
- common TEAEs that equal to or exceed a threshold of 5% in any treatment group.

The number and percentage of subjects with TEAEs, as classified by PT only, will be summarized for each treatment group.

The number of TEAEs and the number and percentage of subjects with TEAEs, as classified by SOC and PT will also be summarized by severity and by relationship to study drug. In the subject count, if a subject has multiple TEAEs with the same SOC or PT, but with differing severity or relationship, then the subject will be counted only once with the worst severity and highest degree of relationship, however, if any of the severity or relationship values are missing then the subject will be counted only once with missing severity or relationship. In the adverse event count, the adverse events will be presented in each category they were classified to. Drug related TEAEs will be presented in a similar way by severity only.

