Adverse events of special interest oral/ facial paresthesia, uterine bleeding and elevation in ALT and/or AST >3 x ULN. A summary table and detailed listing of adverse events of special interest will be provided. A burden of toxicity graph will be generated for the adverse events of special interest.

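### On the default safety set, the uterine-bleeding percentage counts women with a hysterectomy as event-free, so it understates the risk among women with a uterus

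*SAP*

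**What the plan says.** **Eligibility.** Criterion 3 of Protocol 4.1 includes among its routes of entry "having had bilateral oophorectomy ≥6 weeks prior to the screening visit (with or without hysterectomy"). Criteria 7 and 8 require willingness to undergo transvaginal ultrasound and endometrial biopsy, and each adds: "This is not required for subjects who have had a partial (supracervical) or full hysterectomy". The protocol therefore expects such women in the trial and treats the endometrial assessments as not applying to them.

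**The event.** Uterine bleeding is one of three adverse events of special interest in Protocol 9.15 and SAP 7.5.1; the latter lists them as "Adverse events of special interest oral/ facial paresthesia, uterine bleeding and elevation in ALT and/or AST >3 x ULN". Protocol 9.18 lists, among the occasions for biopsy: "In all cases of uterine bleeding".

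**The table.** For these events SAP 7.5.1 says: "A summary table and detailed listing of adverse events of special interest will be provided". It also plans a burden of toxicity graph. It names neither a statistic nor a denominator. Three other statements fill the gap:
- SAP 7.5: "All analyses of safety will be presented by treatment group for SAF, unless specified otherwise".
- SAP 5.1: "The SAF comprises all randomized subjects who received at least one dose of study drug".
- SAP 7.5.1, on adverse events generally: "The number and percentage of subjects with TEAEs, as classified by PT only, will be summarized for each treatment group".

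Nothing gives uterine bleeding its own denominator. SAP 7.5.2.1 does give one to the liver criteria, which count only subjects with at least one value during treatment.

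**Balance.** Protocol 5.3 and SAP 3.3 describe randomly permuted blocks and state no stratification by hysterectomy. SAP 7.2.3 names amenorrhea and bilateral oophorectomy as disease-specific history, but not hysterectomy.

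**The concern.** A percentage is read as a risk, and a risk needs a denominator of people in whom the event is expected to be possible. Women with a hysterectomy add to the SAF denominator and are expected to add little or nothing to the numerator. The tabulated percentage is then too low as a statement about women with a uterus, and the error favours the drug.

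The trial has seven active arms and is meant to choose the Phase 3 dose (Protocol 5.2), so readers will look across the arms of this table for a dose pattern. If the share of women with a hysterectomy differs by chance between arms of 44, part of any visible difference, or of its absence, may come from the denominators. A listing of cases does not help, because it shows who bled and not how many women were at risk.

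**Working it through.** **Inputs from the documents.** 352 women over 8 arms gives 352 / 8 = 44 per arm (SAP 4), taken here as the SAF size per arm. The documents state no uterine-bleeding rate and no hysterectomy share, so there is no plan figure to reproduce.

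**Assumption.** Let h be the share of an arm with a partial or full hysterectomy, assumed to be 5% to 40%. These women are taken to contribute no events.

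**Step 1: dilution.** SAF rate = at-risk rate × (1-h), and the at-risk number per arm = 44 × (1-h). The table uses a 10% at-risk rate as the example. Its last column takes 3 cases in an arm, which is 3/44 = 6.8% on the SAF.

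| h | At risk per arm | 10% at-risk rate tabulated as | 3 cases, % of women at risk |
|---|---|---|---|
| 5% | 41.8 | 9.5% | 7.2% |
| 10% | 39.6 | 9.0% | 7.6% |
| 20% | 35.2 | 8.0% | 8.5% |
| 30% | 30.8 | 7.0% | 9.7% |
| 40% | 26.4 | 6.0% | 11.4% |

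**Step 2: comparison between arms.** Under randomization, hysterectomy status is independent of arm. Every arm has the same expected factor (1-h), so the ratio of at-risk shares between two arms centres on 1.00. Ratios of rates are not systematically biased. Absolute differences shrink by (1-h).

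**Step 3: chance imbalance.** The number with a hysterectomy in an arm is taken as Binomial(44, h). The second column below is exact; the third is from simulation. A gap of 10 percentage points means at least 5 women, since 0.10 × 44 = 4.4.

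| h | P(two given arms differ by 10 points or more) | 95% range of the ratio of at-risk shares |
|---|---|---|
| 5% | 0.03 | 0.91 to 1.10 |
| 10% | 0.11 | 0.86 to 1.16 |
| 20% | 0.23 | 0.81 to 1.24 |
| 30% | 0.30 (0.295) | 0.76 to 1.32 |
| 40% | 0.33 | 0.70 to 1.42 |

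**Step 4: an extreme pair.** At h = 30%, the central 95% range for at-risk women in one arm is 25 to 37. Put one arm at each end with 4 events each. The at-risk rates are 4/25 = 16% and 4/37 = 11%, and the table shows 4/44 = 9% in both. A gap of 12 or more has probability about 0.7% for two given arms, and about 12.5% for the widest gap among eight. Even then, Fisher's exact test of 4/25 against 4/37 gives p = 0.70. This marks the outer edge of the problem and is not a typical case.

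**The case against.** **The SAF percentage is inferred.** The special-interest sentence in SAP 7.5.1 states no percentage and no denominator, SAP 7.1 sends table formats to separate specifications that are not available here, and SAP 7.5 leaves room for exceptions. This is true. But no exception is specified in the SAP, so the plan followed as written yields the SAF percentage.

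**The arms remain comparable.** A reader might infer that a denominator including women without a uterus makes the arms non-comparable. The documents do not support that: allocation is random, so the expected dilution is equal. What stands is chance imbalance, as for any unstratified baseline factor, and the lack of a dedicated summary to check it.

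**The share may be small.** In criterion 3, hysterectomy is mentioned only with the oophorectomy route; the other routes require spontaneous amenorrhea. Read literally, that could hold h well below 20%. At 5% to 10% the effect is slight (10% shown as 9.5% to 9.0%). This stands, and is why the range starts at 5%.

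**These women are not shown to be incapable of the event.** The protocol waives ultrasound and biopsy after partial or full hysterectomy. It does not say that no bleeding can be recorded, and after a supracervical procedure that would be too strong. This stands, so the fix must say where such an event is counted.

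**Part of the information is already planned.** Coded medical history is summarized by arm (SAP 7.2.3), the disease-specific list there is not exhaustive, and special-interest events are listed in detail. This partly stands: coded history may show hysterectomy, but only if it was recorded as such, and nothing links it to the bleeding table.

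**Conclusion.** The point holds, and it is minor. Under the SAF default, the uterine-bleeding percentage understates the risk among women with a uterus by the factor (1-h). For an assumed h of 5% to 40%, a 10% risk is shown as 9.5% to 6%. This rests on two assumptions: the range for h, which the documents do not give, and women with a hysterectomy contributing essentially no events.

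There is no systematic bias between arms. Chance differences in h can distort a comparison of arms of 44, and the SAP plans no specific summary that would let a reader judge this. The tempting conclusion that the table would hide or create a dose pattern goes too far: that needs an extreme imbalance, and with a handful of events per arm neither denominator can establish a pattern. The table is descriptive. No test, power figure, efficacy claim or stopping rule depends on it, and biopsy for bleeding is triggered woman by woman, whatever the denominator.

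**What to change.** 1. In SAP 7.5.1, for uterine bleeding and other uterine or endometrial terms, add n and % by arm among SAF women without a partial or full hysterectomy. This is the grouping that inclusion criteria 7 and 8 already use.
2. Keep n and % on the full SAF as a second line.
3. Report any coded event in a woman with a partial or full hysterectomy on the SAF line, with a footnote. The numerator and denominator of the added line then match and no event is lost.
4. In SAP 7.2.3, name hysterectomy status by arm among the disease-specific baseline summaries.

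The cost is some SAP wording, one derived flag and one extra table line. Sites must already know hysterectomy status to apply the ultrasound and biopsy waivers, so no new assessment should be needed. The reported rate becomes slightly less favourable, and nothing in the efficacy analysis or sample size changes.

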7.5.2 Clinical Laboratory Evaluation

The baseline visit is the last measurement taken prior to initial study drug administration.

Quantitative clinical laboratory variables, i.e. hematology, biochemistry, and urinalysis will be summarized using mean, standard deviation, minimum, median, maximum, 10%, 90%, and lower and upper quartiles for each treatment group at each visit. Additionally, a within-subject change will be calculated as the post-baseline measurement minus the baseline measurement and summarized in the same way. Each laboratory result will be classified as low (L), normal (N), or high (H) at each visit according to the laboratory supplied reference ranges.

Shift tables will be generated for each treatment group at each visit.

Frequency tabulations of qualitative clinical laboratory variables (urinalysis) will be presented for each treatment group at each visit (excluding Visits 2A, 3A, and 4A).

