1.2 Summary of Nonclinical Studies

A series of non-Good Laboratory Practice (GLP) and GLP nonclinical studies were carried out in order to define the pharmacodynamics (PD), pharmacokinetics (PK), and toxicity of the test product ESN364. Compound affinity to human NK3R and to rat and monkey NK3R orthologs were confirmed via in vitro studies. Receptor-ligand affinity for ESN364 has been confirmed as essentially equipotent for the human and monkey NK3R orthologs. Also, the metabolic stability of the test item was determined to be similar in human and monkey liver microsomes. These preliminary studies justified the use of rat and monkey species in nonclinical testing. Since castrate animals exhibit high and stable levels of plasma LH, castrated rats and monkeys were used as the animal model of choice to measure the PD response to ESN364 in the modulation of plasma LH. Rats and monkeys were used for GLP toxicity studies, and monkeys, as the most sensitive species, were used to define the no observed adverse effect level (NOAEL) and to determine the starting dose in the Phase 1 clinical study.

In the nonclinical toxicology studies in rats and monkeys, ESN364 was well tolerated and the NOAEL was considered to be 25 mg/kg/day in Cynomolgus monkeys, the most relevant species; drug exposure (ie, AUC) at this dose level in Cynomolgus monkey was similar to drug exposure levels measured in premenopausal women dosed at 540 mg/day. The main events that were observed in the nonclinical studies were considered to be related to the pharmacology of ESN364, including reduction of the ovarian activity in female monkeys. Adverse events were only observed at the very high doses used in the nonclinical studies. The NOAEL exceeded the intended clinical doses by a factor of 20. In monkeys, high doses of ESN364 resulted in weight loss and histopathological changes such as hyperplasia of lymphocytes in lymph nodes, spleen, and lung, as well as perivascular inflammation in the kidney. In addition, a reduction in platelet counts considered to be due to decreased production in bone marrow resulted in observations of hemorrhage and regenerative anemia; these effects were recoverable with discontinuation of dosing. In rats, very high dose levels were associated with death and marked clinical signs (including lethargy, reduced activity, labored respiration, and staggering), and body weight loss during the first few days of treatment.

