4.4 Withdrawal Criteria

Subjects have the right to withdraw from the study at any time for any reason, including personal reasons. A subject can withdraw without giving a reason. This will not affect the subject's future care. The Investigator should, however, try to find out why a subject has withdrawn from the study and document the reason for withdrawal in the source documents and on the electronic Case Report Form (eCRF).

A subject **must** be withdrawn from the study or treatment for any of the following reasons:

- Withdrawal of informed consent;
- Lost to follow-up;
- If, for safety reasons, including meeting the requirement for interruption of study drug, it is in the best interest of the subject that she be withdrawn, in the Investigator's opinion;
- Development of a medical condition that requires concomitant treatment with a prohibited therapy (see Section 5.6);
- Development of seizures or other convulsive disorders;
- Breaking of the randomization code during administration of the study drug by the Investigator or by a member of the site staff. If the code is broken by the Sponsor for safety reporting purposes or early timepoint analysis, the subject may remain in the study;
- Confirmed decrease in platelets below 75,000 mm³, which does not normalize after 7 days;
- ALT or AST >8 × ULN;
- ALT or AST >5 × ULN for more than 2 weeks;

- ALT or AST $>3 \times$ ULN **AND** total bilirubin $>2 \times$ ULN or International Normalized Ratio (INR) $>1.5 \times$ ULN; or
- ALT or AST $>3 \times$ ULN with the appearance of fatigue, nausea, vomiting, right upper quadrant pain or tenderness, fever, rash, and/or eosinophilia ($>5\%$).

See Appendix D and Section 9.14 for the procedure to follow in case of suspected drug-induced liver injury (DILI).

In the event that a subject is withdrawn from the study drug, the Medical Monitor and Sponsor or designee should be informed. In the event of withdrawal due to a serious adverse event (SAE), the Sponsor should be notified within 24 hours (for details on adverse event reporting see Section 9.3). In the event of withdrawal for other reasons, the Sponsor or designee should be notified within 2 days of the event.

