9.4 Stopping Rules or Discontinuation Criteria

The study may be stopped for any of the following reasons:

- If ≥ 3 subjects are withdrawn from the study due to a confirmed study-related increase in:
 - ALT or AST $> 8 \times$ ULN;
 - ALT or AST $> 5 \times$ ULN for > 2 weeks;
 - ALT or AST $> 3 \times$ ULN **AND** total bilirubin $> 2 \times$ ULN or INR $> 1.5 \times$ ULN; or
 - ALT or AST $> 3 \times$ ULN with the appearance of fatigue, nausea, vomiting, right upper quadrant pain or tenderness, fever rash, and/or eosinophilia ($> 5\%$);
- If ≥ 3 subjects are withdrawn from the study due to a confirmed study-related decrease in platelets below 75,000 mm³, which does not normalize after 7 days;

- If ≥ 2 subjects develop seizures or other convulsive disorders that are not readily attributable to another underlying disease (eg, brain tumor, head trauma); or
- If an increased frequency of unanticipated deaths or other SAEs is observed.

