9.7 Clinical Laboratory Evaluations

Blood samples for clinical laboratory tests will be collected at each visit. Urine samples for urinalysis will be collected at each visit (excluding Visits 2A, 3A, and 4A).

Blood samples will be collected and handled as specified in the central laboratory manual. Except for Visits 2A, 3A, and 4A, all blood samples for clinical laboratory tests should be taken in a fasted state (defined as nothing by mouth except water [up to 1 hour before study drug intake] for at least 10 hours).

Standard laboratory tests will be performed by the central laboratory. Further procedures for sample collection, shipment, processing, and storage are described in the laboratory manual provided by the central laboratory.

The following clinical laboratory tests will be performed on the samples (see Appendix B):

- Biochemistry: sodium, potassium, uric acid, creatinine, calcium, AST, ALT, blood urea nitrogen, eGFR, chloride, inorganic phosphorus, bicarbonate, lactate dehydrogenase, alkaline phosphatase, gamma-glutamyl aminotransferase, albumin, glucose, total bilirubin, creatine kinase, and total protein;
- Coagulation (at the screening visit and Week 12 [Visit 5]/ET only): INR and activated partial thromboplastin time; and
- Hematology: white blood cell count with differential (neutrophils, lymphocytes, eosinophils, monocytes, and basophils), hemoglobin, hematocrit, red blood cell count, and platelets.

Serology (HBsAG, HCV, and HIV antibodies) will be completed at the screening visit.

Urinalysis will be performed on site using a commercial urine dipstick. In the event the dipstick result is positive, a urine sample must be shipped to a central laboratory for urine sediment analysis (see Appendix B for list of urinalysis analytes).

Urine drug screen for amphetamines, benzodiazepines, tricyclic antidepressants, cannabinoids, cocaine, or opiates will be performed at the screening visit. Note that testing positive for cannabinoids will not exclude a subject from participating the study. A subject with an active prescription for opiates may also participate in the study at the discretion of the Investigator.

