2.0 INTRODUCTION

Hepatotoxicity is injury or damage to the liver that may be associated with impaired liver function (Navarro and Senior 2006). Drug-induced hepatotoxicity is one of the most common causes of termination of drug development, a major reason for refusal of market authorization and for restricted use, and the single most important cause of the withdrawal of market authorization for products (Björnsson 2006). Thus, drug-induced hepatotoxicity is a major concern during the discovery, development to post-authorization phases of the product life cycle (excerpted from Draft Guidance Document, Hepatotoxicity of Health Products, Ministry of Public Health, Canada, December 2010).

As stated in the United States Food and Drug Administration (FDA) "Guidance for Industry - Drug-Induced Liver Injury: Premarketing Clinical Evaluation"; hepatocellular injury (usually detected by serum aminotransferase elevations [AT]) can be caused by drugs that rarely, if ever, cause severe DILI (e.g., aspirin, tacrine, statins, and heparin), as well as by drugs that do cause such injury. The frequency of serum AT elevations also is not a good indicator of a potential for severe DILI because drugs such as tacrine (not a cause of severe DILI) can cause AT elevations in as many as 50 percent of patients. Very high levels of observed ATs may be a somewhat better indicator of potential for severe DILI, but the most specific indicator is evidence of altered liver function accompanying or promptly following evidence of hepatocellular injury.

The single clearest (most specific) predictor found to date of a drug's potential for severe hepatotoxicity, is the occurrence of hepatocellular injury (AT elevation) accompanied by increased serum total bilirubin (TBL) not explained by any other cause, such as viral hepatitis or exposure to other hepatotoxins, and without evidence of cholestasis, together with an increased incidence of AT elevations in the overall trial population compared to control. Increased plasma prothrombin time, or its international normalized ratio (INR), a consequence of reduced hepatic production of Vitamin K-dependent clotting factors, is another potentially useful measure of liver function that might suggest the potential for severe liver injury.

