- g. Includes age, race, sex, and smoking status (smoker/non-smoker).
- h. Includes height (at the screening visit only), weight and waist circumference. A bimanual clinical pelvic and clinical breast examination will be performed at the screening visit. A bimanual clinical pelvic examination can be performed at any time in the study where clinically indicated.
- i. Weight and waist circumference only.
- j. Includes biochemistry, coagulation (at the screening visit and Week 12 [Visit 5]/ET only), and hematology panel. Blood samples for clinical laboratory tests should be taken in a fasted state (defined as nothing by mouth except water for 10 hours), except for Week 2 (Visit 2A), Week 6 (Visit 3A), and Week 10 (Visit 4A).
- k. Includes biochemistry and hematology, only.
- l. Includes oral/tympanic temperature, sitting blood pressure, and pulse rate (supine after 5 minutes of rest).
- m. All 12-lead ECGs will be captured in triplicate (ie, 3 separate 12-lead ECGs at least 1 to 2 minutes apart within a 5-minute window). The subject should rest in supine position for at least 10 minutes prior to the first ECG.
- n. Only in the event the subject does not have a normal/negative or no clinically significant findings Pap smear from previous 9 months on record.
- o. Subjects will undergo endometrial biopsy at Screening (if endometrial thickness is ≥ 4 mm), at Week 12 (end-of-treatment)-(all subjects), at the ET Visit for subjects who are withdrawn from the study prior to completion (if study drug exposure is ≥ 10 weeks), and in all cases of uterine bleeding. If the uterine biopsy is abnormal at Week 12 (end-of-treatment), subjects will have a repeat biopsy 4 weeks later, if clinically indicated.
- p. For HBsAG, anti-HCV antibodies, and anti-HIV antibodies.
- q. Samples will be taken predose at Day 1 (Visit 2), Week 8 (Visit 4), and Week 12 (Visit 5)/ET, as well as predose and 3 hours postdose at Week 4 (Visit 3). The Week 4 (Visit 3) 3 hours postdose PD sample should be shifted to a later date in cases where the subject cannot accommodate the PK sampling schedule at that visit. The PD sample should be taken at the same time as the 3-hour postdose PK sample (see Section 8.2). A PD sample will be taken at the follow-up visit (Week 15 [Visit 6]) as well. Markers include LH, FSH, E2, and SHBG.

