6.2 Safety Variables

Safety variables will include the following:

- Incidence and severity of treatment-emergent adverse events (TEAEs);
- Endometrial health assessment (transvaginal ultrasound ± endometrial biopsy);
- Vital signs (sitting systolic and diastolic blood pressure and pulse rate);
- Laboratory tests (hematology, biochemistry, urinalysis, and coagulation);
- 12-lead electrocardiogram (ECG) parameters;
- Plasma bone density marker concentrations;

- Physical examinations; and
- Columbia Suicide Severity Rating Scale (C-SSRS).

A TEAE is defined as an adverse event observed after starting administration of study drug through 7 days after the last dose of study drug. If the adverse event occurs on the day of the first dose and the onset time is on or after the time of the first dose of study drug or the onset time is missing, then the adverse event will be considered treatment emergent. If the adverse event occurs on the day of first dose and the onset time is before the time of the first dose of study drug, then the adverse event will not be considered treatment emergent. If a subject experiences an event both during the pre-investigational period that continues into the investigational period, the event will be considered as TEAE only if it has worsened in severity (i.e. it is reported with a new start date).

A drug-related TEAE is defined as any TEAE related to study treatment as assessed by the investigator or with missing assessment of the causal relationship.

Other safety endpoints will be considered treatment emergent if observed after starting administration of study drug through 1 day after the last dose of study drug.

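### SAP 7.5.2 leaves out coagulation, a safety variable declared in SAP 6.2, and the SAP liver table counts by arm only the bilirubin branch of the protocol's liver criterion

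*SAP*

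**What the plan says.** SAP 6.2 lists the laboratory safety variables as "Laboratory tests (hematology, biochemistry, urinalysis, and coagulation". Protocol 9.7 sets out the collection: "Coagulation (at the screening visit and Week 12 [Visit 5]/ET only): INR and activated partial thromboplastin time". The SAP repeats that timing in a footnote to its own schedule (SAP 2.2): "Includes biochemistry, coagulation (at the screening visit and Week 12 [Visit 5]/ET only), and hematology panel". Appendix B of the protocol also lists prothrombin time under coagulation.

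The analysis section, SAP 7.5.2, opens with "Quantitative clinical laboratory variables, i.e. hematology, biochemistry, and urinalysis will be summarized using mean" and the other descriptive statistics, by treatment group and visit. Change from baseline is summarized in the same way. The section then provides for low/normal/high classification of laboratory results and for shift tables by treatment group.

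SAP 7.5.2.1 tabulates ALT, AST, ALP, total bilirubin and combinations of them by arm, and adds a listing of women with suspected drug-induced liver injury.

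The protocol uses INR in its liver rules. The withdrawal criteria (Protocol 4.4) pair ALT or AST above 3 x ULN with "total bilirubin $>2 \times$ ULN or International Normalized Ratio (INR) $>1.5 \times$ ULN". The study stopping rule (Protocol 9.4) uses the same pairing, "total bilirubin $> 2 \times$ ULN or INR $> 1.5 \times$ ULN", and so does the suspected-DILI definition in Protocol 9.14.2.

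**The concern.** A variable that the SAP declares for safety should have a stated analysis, and coagulation does not clearly have one. The list in 7.5.2 is introduced by i.e., not e.g., so a programmer who follows it would produce tables for three panels and stop. The SAP's own record of departures from the protocol (Section 8) does not mention coagulation, which suggests an oversight and not a decision.

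The gap matters most for the liver. The introduction to Appendix D says of a raised prothrombin time or INR that it "is another potentially useful measure of liver function that might suggest the potential for severe liver injury". The trial's liver criterion has two branches, one on bilirubin and one on INR, and only the first has a planned count by arm. In an eight-arm dose-ranging trial meant to choose a Phase 3 dose, a reader would want to see from the tables how often the full criterion was met at each dose. The planned tables do not show that.

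**Working it through.** The plan states no figure to reproduce. The check sets what is declared and collected beside what is analysed.

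**1. Panels declared and panels summarized**

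| Panel | Declared in SAP 6.2 | Descriptive and change-from-baseline summary in SAP 7.5.2 |
|---|---|---|
| Hematology | yes | yes |
| Biochemistry | yes | yes |
| Urinalysis | yes | yes |
| Coagulation | yes | not named |

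Declared 4, named for summary 3, so 4 - 3 = 1 panel lacks a specified summary. SAP 7.5.6, on other safety observations, does not pick it up.

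**2. Branches of the liver criterion and rows in SAP 7.5.2.1**

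| Component | In Protocol 4.4, 9.4 and 9.14.2 | By-arm row in SAP 7.5.2.1 |
|---|---|---|
| ALT or AST >3 x ULN alone | part of the criterion | yes |
| with total bilirubin >2 x ULN | yes | yes |
| with INR >1.5 x ULN | yes | no |

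INR rows in the liver table: 0.

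**3. Amount of data**

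- Planned randomization: 8 arms x 44 women = 352, so at most 352 pairs of screening and Week 12/ET values.
- The protocol sizes the trial for about 10% discontinuing, with 40 of 44 per arm remaining: 8 x 40 = 320 women. Some of the other 32 would have an early termination sample. However, SAP 7.5 restricts safety analyses to data up to one day after the last dose, apart from adverse events and follow-up visit data, so later early termination samples may fall outside.
- Scheduled post-baseline coagulation values per woman: 1. Unscheduled values, for example from a liver work-up under Appendix D, come on top.

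**4. Baseline**

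The Day 1 procedures (Protocol 6.3.1) name biochemistry and hematology but not coagulation. Under the SAP 7.5.2 baseline definition (the last value before first dose), the screening sample normally serves. A change-from-baseline table is feasible without new data.

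**The case against.** The strongest reply is that coagulation may be covered after all. In SAP 7.5.2 the closed list governs the sentence on descriptive statistics. The later sentence on low/normal/high classification refers to laboratory results in general, and the shift tables follow from it. Since SAP 6.2 counts coagulation as a laboratory test, those tables can be read to include INR and aPTT. Protocol 10 also promises tables, figures and listings for all collected data, Protocol 10.2.2 promises laboratory tests over time, and the separate table specifications cannot be seen here. This stands in part: it would be wrong to infer that no coagulation value enters any table. But coagulation is not named in the shift-table text. Even on the generous reading there is no value summary, no change from baseline and no count at the protocol's INR threshold.

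A second reply is that the liver signal is mostly captured. In Protocol 4.4, 9.4 and 9.14.2 the INR limit applies only together with ALT or AST above 3 x ULN. A woman in that branch therefore already counts in the by-arm ALT/AST rows and in the summary of adverse events of special interest. Suspected DILI cases are listed, and clinically significant laboratory abnormalities are to be reported as adverse events. This also stands. What is missing is the separate count for the INR branch, which none of these outputs supplies.

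Two stronger readings are tempting and do not hold. A reader might infer that INR is the only measure of hepatic synthetic function collected. It is not: albumin is in the biochemistry panel (Protocol 9.7, Appendix B) and is summarized by arm. A reader might also connect the point to the monkey studies, where Protocol 1.2 reports a change that "resulted in observations of hemorrhage and regenerative anemia". That sentence attributes the finding to reduced platelet counts, and platelets are in the hematology panel, which SAP 7.5.2 does summarize.

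**Conclusion.** The point holds as an inconsistency within the SAP plus one missing count. Coagulation is declared in SAP 6.2, is given no descriptive or change-from-baseline summary by arm in SAP 7.5.2, and has uncertain status in the shift tables. SAP 7.5.2.1 counts the bilirubin branch of the protocol's liver criterion by arm but not the INR branch.

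Its size is one of four laboratory classes, one scheduled post-baseline value per woman, and at most about 352 pairs before dropout. The effect is on completeness of safety reporting only. No efficacy conclusion depends on it, and the withdrawal and stopping rules operate on individual results during the trial whatever the SAP tabulates.

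The conclusion assumes that the list in 7.5.2 is meant as written and that the unseen table specifications do not already add coagulation. If they do, the SAP text still needs to agree with them. It also takes the INR branch as conditional on ALT or AST, as in Protocol 4.4, 9.4 and 9.14.2. The punctuation in Appendix D, Section 3.0 is looser, and the sponsor should reconcile it with those sections. The correction is worth making because it costs almost nothing.

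**What to change.** In SAP 7.5.2, extend the list to hematology, biochemistry, coagulation (INR, aPTT, and PT if reported) and urinalysis. State that coagulation gets the same tables of values, change from baseline and low/normal/high shift, from screening to Week 12/ET.

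In SAP 7.5.2.1, add two by-arm rows: INR >1.5 x ULN, and ALT or AST >3 x ULN with INR >1.5 x ULN. Apply the existing footnote on values taken the same day or up to one day apart to the combined row. State that unscheduled INR values count, and that the denominator is women with at least one INR value in the treatment period. Both rows repeat a threshold already in the protocol, so no clinical rule is altered.

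The cost is a few words, two table rows and one more standard set of laboratory tables. No new samples, visits or data are needed. The change can be made before database lock and unblinding.
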